9.4.3 ANALYSIS OF THE SECONDARY ENDPOINT(S)

Secondary endpoints are not dependent on primary outcomes but rely on standardized scales for mental health measures. Weight will be measured in kilograms. We will examine both absolute

changes in the weight level as well as percentage changes in weight. Economic measures will generally be measured in local currency to allow for standardization. Secondary measures are also generally repeated, with the exception of weight which is only captured at baseline and endline The same regression approach will be used for secondary outcomes as described above for primary outcomes.

9.4.4 SAFETY ANALYSES

N/A

9.4.5 BASELINE DESCRIPTIVE STATISTICS

A baseline balance table comparing demographics (e.g. age, assets), baseline measures of primary outcomes, and baseline measures of economic covariates will be generated prior to the analysis. The table will include means and standard deviations by group as well as p-values for tests of equality between each treatment arm and the control.

9.4.6 PLANNED INTERIM ANALYSES

N/A

9.4.7 SUB-GROUP ANALYSES

While there are reasons to expect that the effects of income instability may vary with age, we are not aware of any prior evidence that strongly suggests the effects may vary by race or ethnicity. Nonetheless, because these effects are of interest, we will augment our primary regression specification – detailed above – to study heterogeneous treatment effects along a number of key dimensions. This analysis will include the covariate of interest (main effect) and its interaction with each of the treatment dummies (interaction effects) to assess which individuals are affected the most by income instability. This is a standard and unbiased statistical analysis to compare whether covariates of interest modify the effects of income instability. This assessment will include baseline covariates likely to moderate the impact of the instability (including age, baseline levels of psychological health and of assets). Given the racial homogeneity of the anticipated study population, no heterogeneity analysis is planned for racial differences at this time.

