4.2 SCIENTIFIC RATIONALE FOR STUDY DESIGN

The study was designed to allow us to both: 1) identify the effect of income instability on mental health. For this, it is crucial to hold average income constant when varying income instability. And 2) decompose the effects of predictable and unpredictable instability and compare them to the effect of increasing the level of income, we will compare the outcomes in the predictable and unpredictable arms to the stable income and control arms. Additionally, we will isolate the effect of *ex-ante* income uncertainty by comparing participants who have *ex-post* identical income realizations. Each of these analyses are explained in greater detail below.

Effect of Level. We will estimate this effect by comparing the Control and Stable Income arms. The study earnings of both of these arms will be stable over time.

Effect of Predictable Instability. We will estimate this effect by comparing the Stable Income and Predictable Instability arms. While the two arms will earn on average the same, the earnings of the Predictable Instability arm will vary over time while those of the Stable Income arm will not.

Effect of Unpredictable Instability. We will estimate this effect by comparing the Predictable Instability and Unpredictable Instability arms. While the Predictable Instability arm has a known average, the Unpredictable Instability arm will earn the same amount *in expectation*. The difference between them is that a Predictable Instability participant can anticipate the swings in her future income while the incomes of Unpredictable Instability participants are unpredictable. As discussed before, this difference between the two arms has two consequences. One is the *exante* income uncertainty, i.e., the Predictable Instability participant knows what to expect while the Unpredictable Instability does not. The other is that an Unpredictable Instability participant may have an income realization which is different from what she initially expected.

We explain next how our design permits separately estimating these two distinct consequences of unpredictable instability.

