9.2 SAMPLE SIZE DETERMINATION

Given IPAs' performance on similar previous surveys during the lean season (when respondents are relatively available), we assume a uniform 5% attrition across all arms.

We will recruit 2,267 participants. 1,067 will be assigned to the Unpredictable Instability arm and 400 to each one of the other three study arms. About 37.5% of the Unpredictable Instability arm (i.e., 400 individuals) are expected to have Neutral 4-period schedules, such that the estimation of the effect of ex-ante income uncertainty corresponds to a randomized controlled trial with a sample size of 760 (95% of 800) equally split between "treatment" and "control". For a two-tailed test with 0.05 significance level and 0.8 power, the minimum detectable effect (MDE) is 0.2 of a standard deviation (SD) for each primary outcome (calculations done in Stata). These effect sizes are consistent with those found in the literature on the effects of cash transfers in low-income settings (e.g., Haushofer & Shapiro, 2016 & 2018; McIntosh & Zeitlin, 2020). Similarly, the MDE for the effect of predictable income volatility is also 0.2 SD. The estimation of the effect of income risk, which corresponds to RCT where 72.7% of the 1,394 (95% of 1,467) participants are assigned to the treatment condition, has an MDE of 0.17 SD. The estimation of the effect of income realizations has an MDE of 0.19 SD if those with unlucky and lucky schedules are grouped together and of 0.23 SD if they are each compared separately to those with Neutral schedules. For panel data analyses, standard errors will be clustered at the individual level (the unit of randomization) (Abadie et al. 2017). These are conservative estimates that consider data from the follow-up survey only; they ignore that we will have baseline measures of all outcomes of interest, which should substantially reduce MDEs, and that we will have repeated measures of most outcomes. In addition to an index of mental health, given the rapid evolution of multiple hypothesis testing techniques, will we use state of the art techniques to adjust for multiple hypothesis testing.

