9.4 STATISTICAL ANALYSES

9.4.1 GENERAL APPROACH

To study the effects of uncertainty, we will compare the outcomes of participants assigned to the Unpredictable Instability arm to the outcomes of participants assigned to the Predictable Instability arm, while holding the payment schedule constant. Similarly, to study the effects of predictable income volatility, we will compare the outcomes of participants assigned to the Predictable Instability arm to the outcomes of participants assigned to the Stable Income arm. Finally, we will estimate the effects of a stable income by comparing the outcomes of participants assigned to the Control arm.

For each of the individual outcomes, the primary regression model will be:

$$Y_{it} = \lambda_0 + \sum_{\{k=1\}}^3 \lambda_1^k T_i^k + \lambda_2 X_i + \lambda_3 Y_{i0} + \gamma_t + \epsilon_{it}.$$

where *i* indexes the individual; Y_i is individual *i*'s outcome in the post-treatment period *t*; T_i^k is an indicator for treatment arm k; X_i is a vector of individual-level controls (e.g., age); Y_{i0} is the dependent variable at baseline; and; ϵ_i is the error term. Period fixed effects (γ_t) are also included to control for period effects. The analysis considers treatment assignment as the independent variable, regardless of compliance (i.e., intent-to-treat). We utilize an ANCOVA regression model. Standard errors are clustered by individual. λ_1 are the key coefficients of interest and can be interpreted as the causal effect of each treatment relative to the control group. Additional comparisons between treatments will be conducted to parse the impacts of predictable and unpredictable volatility. Also, to study if outcomes fluctuate together with income, we will compare participants from a given arm with different current study earnings (but who had identical earnings in the past). Given the rapid evolution of multiple hypothesis testing.

A pre-analysis plan will be registered after the pilot but prior to the main study with any updates to this analysis plan based on learnings from the pilot.

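### The treatment-by-covariate interactions in section 9.4.7 are measured against Control, so for the volatile arms they mix moderation of the income-level effect with moderation of the instability effect; instability moderation should be read from contrasts between interactions

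*Combined protocol and SAP*

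**What the plan says.** All references are to the combined protocol and SAP.

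- Section 9.4.7 augments the primary regression with the covariate of interest and "its interaction with each of the treatment dummies (interaction effects) to assess which individuals are affected the most by income instability". Age, baseline psychological health and assets are the named covariates. It adds: "This is a standard and unbiased statistical analysis to compare whether covariates of interest modify the effects of income instability". It names no contrast between interaction coefficients.
- Section 9.4.1 sets up that regression with three treatment indicators. Their coefficients "can be interpreted as the causal effect of each treatment relative to the control group", so Control is the omitted arm. The section also promises further comparisons between treatments, to separate predictable from unpredictable volatility, but does not say whether these extend to the interactions.
- Section 4.2 and its Table 4 define the effects. The level effect is Stable against Control. For predictable instability: "We will estimate this effect by comparing the Stable Income and Predictable Instability arms". Unpredictable instability is Unpredictable against Predictable. Control enters neither instability effect.

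**The concern.** The design holds average income constant across the treated arms so that instability can be separated from income level. An interaction measured against Control, which gets no programme work, joins the two again. The covariates named in 9.4.7 make this more than a formality: women with few assets or poor baseline mental health might plausibly gain more, or less, from any paid work.

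Two errors could follow if the volatile-arm interactions are read as 9.4.7 describes. A covariate that changes only the response to extra income could be reported as identifying who is harmed by instability. Conversely, section 9.1 expects income to help and instability to erode the gain, so a group more sensitive to both would have interactions of opposite sign that partly or wholly cancel, and real moderation of the instability effect could be missed. Moderating factors are part of secondary objective 2; no primary comparison is affected.

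**Working it through.** **What each coefficient estimates.** Let L be the covariate's moderation of the level effect, I_P its moderation of predictable instability, and I_U its moderation of the further step to unpredictability. With Control as reference:

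- Stable × X = L
- Predictable × X = L + I_P
- Unpredictable × X = L + I_P + I_U

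Subtracting:

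- Predictable × X minus Stable × X = I_P
- Unpredictable × X minus Predictable × X = I_U
- Unpredictable × X minus Stable × X = I_P + I_U

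The contrasts are free of L; the two volatile-arm interactions are not.

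**Inputs.** Section 9.2 gives 400/400/400/1,067 randomised and 5% attrition in every arm: 0.95 × 400 = 380 and 0.95 × 1,067 ≈ 1,014. The error rates are stated: "For a two-tailed test with 0.05 significance level and 0.8 power".

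**Reproducing the plan's figures.** MDE = (1.960 + 0.842) × √(1/n1 + 1/n2), in SD units.

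- 380 v 380: 2.802 × 0.0725 = 0.203. The plan says "the minimum detectable effect (MDE) is 0.2 of a standard deviation (SD) for each primary outcome" for the ex-ante uncertainty comparison, and "the MDE for the effect of predictable income volatility is also 0.2 SD". Agrees after rounding.
- 380 v 1,014: 2.802 × 0.0601 = 0.169. The plan says "72.7% of the 1,394 (95% of 1,467) participants are assigned to the treatment condition, has an MDE of 0.17 SD". Agrees.

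The plan states no power or MDE for any interaction.

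**Standard errors of the interactions.** For a covariate scaled to SD 1, residual SD 1, one follow-up round and no baseline adjustment, the SE is again √(1/n1 + 1/n2):

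- Predictable × X v Control: 0.0725; Predictable minus Stable: 0.0725.
- Unpredictable × X v Control: 0.0601; Unpredictable minus Predictable, or minus Stable: 0.0601.

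Rejection rate = Φ(d/SE − 1.96) + Φ(−d/SE − 1.96), with d the true value of the coefficient or contrast.

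**Level moderation only (I_P = I_U = 0; L assumed).**

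| L, SD per SD of X | Predictable × X | Unpredictable × X | Contrasts |
|---|---|---|---|
| 0 | 5% | 5% | 5% |
| 0.05 | 10.6% | 13.2% | 5% |
| 0.10 | 28.1% | 38.3% | 5% |
| 0.15 | 54.3% | 70.3% | 5% |
| 0.20 | 78.7% | 91.4% | 5% |

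For a covariate split 50/50, these rows correspond to differences between the halves of 0, 0.1, 0.2, 0.3 and 0.4 SD. A simulation of the regression with a 0.4 SD difference (2,000 runs) gave 78% and 91% for the two interactions. The contrasts gave 4.4% (Predictable minus Stable), 6.0% (Unpredictable minus Stable) and 4.6% (Unpredictable minus Predictable).

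**Opposite signs (same instability moderation in both volatile arms, so I_U = 0; sizes assumed).**

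| L | I_P | Predictable × X | Predictable − Stable | Unpredictable × X | Unpredictable − Stable |
|---|---|---|---|---|---|
| +0.10 | −0.10 | 5% | 28.1% | 5% | 38.3% |
| +0.10 | −0.20 | 28.1% | 78.7% | 38.3% | 91.4% |
| +0.20 | −0.20 | 5% | 78.7% | 5% | 91.4% |

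In every row Unpredictable minus Predictable rejects about 5%, correctly, because no extra moderation from unpredictability was assumed.

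**No level moderation (L = 0).** Predictable × X and Predictable minus Stable have the same target and power, as do Unpredictable × X and Unpredictable minus Stable.

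**The case against.** The best reply is that 9.4.7 describes a model, not a decision rule. It does not say that each interaction will be tested against zero and interpreted alone. Stable × X is in the regression, so every between-arm moderation contrast can be estimated from it without bias. Section 9.4.1 frames its comparisons as Predictable against Stable and Unpredictable against Predictable and promises between-treatment comparisons, which could be carried into the augmented model. A registered pre-analysis plan may also spell this out.

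Much of this stands. A reader might infer that the regression itself is wrong or biased; it is not. The fault lies in which coefficients are named as the answer. But 9.4.7 attributes the instability reading to the interactions with the dummies themselves, and nothing in it carries the between-treatment comparisons over. The pre-analysis plan is not among the documents and does not settle what 9.4.7 now says.

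The second reply concerns size, and it also stands. The rates rest wholly on assumed moderation. At 0.05 SD per SD the false-flag rates are only about 11% and 13%. The top value, 0.20, equals the plan's whole main-effect MDE of 0.2 SD: were the average level effect 0.2 SD, it would vanish one SD to one side of the covariate mean and double one SD to the other.

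Third, interactions against Control do answer a legitimate question: who gains more or less from each arm as a whole. They need the right label.

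**Conclusion.** The point holds in conditional form. As written, 9.4.7 names coefficients that target level moderation plus instability moderation and describes them as showing instability moderation. That is a mismatch with section 4.2, and more than a missing detail. Whether it misleads depends on the covariate moderating the level effect, which is plausible for baseline assets or mental health but is not quantified in the documents. Over assumed level-only moderation of 0.05 to 0.20 SD per SD, false flags are about 11–79% (Predictable) and 13–91% (Unpredictable), against 5% for the contrasts. The calculation uses one round without baseline adjustment; adjustment and repeated rounds would shrink the standard errors, raising the false-flag rates and leaving the contrasts at 5%.

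Three stronger readings are not supported:

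- That the plan will produce false moderators. With no level moderation, the planned interactions are valid for each volatile arm's instability effect relative to Stable.
- That power to detect instability moderation is lost altogether. A fall to 5% needs exact cancellation; with +0.10 and −0.20 the Predictable interaction still rejects 28%, against 79% for the contrast.
- That the 91% in the cancelling case belongs to Unpredictable minus Predictable. It belongs to Unpredictable minus Stable.

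**What to change.** Keep the regression. In 9.4.7, or in the pre-analysis plan with a matching correction to 9.4.7:

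1. Base statements about moderation of predictable instability on Predictable × X minus Stable × X, and of unpredictable instability on Unpredictable × X minus Predictable × X.
2. Where overall instability in the Unpredictable arm is of interest, use Unpredictable × X minus Stable × X.
3. Report Stable × X as moderation of the income-level effect. If the other two interactions against Control are shown, label them as moderation of the arm's total effect.
4. Reword the sentence claiming unbiasedness so that it refers to these contrasts.

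The cost is two or three linear-contrast commands after the same fit and a short wording change. No new data are needed. Precision is essentially unchanged: 380 v 380 for Predictable minus Stable, and 1,014 v 380 for either Unpredictable contrast, as in the corresponding comparisons with Control.

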9.4.8 TABULATION OF INDIVIDUAL PARTICIPANT DATA

Data will be collected by both individual and timepoint. The final dataset that is released will be structured as a panel with the individual-period as the row and the covariates and outcomes as columns.

9.4.9 EXPLORATORY ANALYSES

Exploratory analyses will be noted in the pre-analysis plan developed after the pilot.

10 SUPPORTING DOCUMENTATION AND OPERATIONAL CONSIDERATIONS

10.1 REGULATORY, ETHICAL, AND STUDY OVERSIGHT CONSIDERATIONS

10.1.1 INFORMED CONSENT PROCESS

10.1.1.1 CONSENT/ASSENT AND OTHER INFORMATIONAL DOCUMENTS PROVIDED TO PARTICIPANTS

All households screened for participation provide verbal consent for the screening.

Participants considering enrollment in the RCT will complete a more detail informed consent procedure. Consent forms describing in detail the study intervention, study procedures, and risks will be given to the participant and written documentation of informed consent will be completed prior to starting the study intervention. All consent materials will be read to the study participant, given that literacy cannot be assumed in the study population. Participants will sign or fingerprint the consent form to indicate their agreement to participate. The following consent materials are submitted with this protocol:

- Informed consent Information sheet, to be given to participant
- Statement of consent, to be signed and kept on file

10.1.1.2 CONSENT PROCEDURES AND DOCUMENTATION

We will conduct a household survey following a random sampling procedure in each village to identify eligible individuals. If eligible and interested, the prospective participant completes the informed consent procedure, which includes the following information:

- Participants are free to exit the study at any time without repercussions and no event would preclude participants from continuing their participation if they desire to do so.
- Participants can choose not to answer questions asked by the surveyor
- Random assignment to study conditions
- Study activities, duration, weekly time commitment, and compensation
- Confidentiality, risks, and benefits from participating

The surveyor will read the informed consent document to the prospective participant, ask comprehension questions, explain or clarify any points of misunderstanding, and ask the individual if she would like to participate in the study. The document is read to the prospective participants given the low literacy levels of many in this setting. Participants will be asked to consent with a signature or fingerprint for those who cannot sign their name. The consent document will be written in the local language and all consent procedures, surveys, and activities

will be conducted by surveyors fluent in that language. To ensure that the translation of the consent forms, surveys, and other study materials is accurate, once the study documents are translated, a local Research Associate will check the accuracy of the translation of all documents one by one by back-translating the documents (without having seen the original) and then discussing and resolving any points of confusion. All study staff will have completed a Human Subjects training and have certificates documenting this process. The surveyors will also be thoroughly trained in survey and activity administration. Finally, all participants will be provided with the phone number to a study hotline that they can call or text if they have questions.

10.1.2 STUDY DISCONTINUATION AND CLOSURE

This study may be temporarily suspended or prematurely terminated if there is sufficient reasonable cause. Written notification, documenting the reason for study suspension or termination, will be provided by the suspending or terminating party to the funding agency and regulatory authorities. If the study is prematurely terminated or suspended, study participants will be contacted, as applicable, and be informed of changes to study visit schedule.

Circumstances that may warrant termination or suspension include, but are not limited to:

- Determination of unexpected, significant, or unacceptable risk to participants
- Insufficient compliance of study staff to the protocol (i.e., significant protocol violations)
- Data that are not sufficiently complete and/or evaluable
- Determination of futility

The study may resume once concerns about safety, protocol compliance, and data quality are addressed, and satisfy the funding agency, IRB, and DSMB.

10.1.3 CONFIDENTIALITY AND PRIVACY

Protection of Subject Privacy

All in-person surveys will be administered in or near the participants' home. The surveyors are trained to seek out a location that provides the most privacy possible for the respondent. For example, they may suggest sitting in the shade of a nearby tree rather than in the house. However, the final location of the survey is left to the participant to decide as they are most able to judge what makes them comfortable. Additionally, phone-based surveys will be designed to minimize the amount of information disclosed (e.g. asking a participant to respond with the number of the appropriate option or point to a visual scale rather than the answer itself for sensitive questions).

Data Management and Security

Beyond the steps taken to protect participant privacy in collecting the data, a large number of steps are taken to maintain the confidentiality of the data once collected. For example, all data is stored under a participant study ID rather than the individual's name. Further, the data is stored on an encrypted server or laptop and only the Research Associates and site investigator will have the password used to decrypt the data or link the data to the participant's name.

Enumerators and their supervisors have access to contact information during the study administration so they can locate participants. At the interviews, the participant's information will be cross-checked with the original roster data and the data will be entered using the participant's unique identifier. All the data will be labeled with the unique identifiers. Identifying information will be removed from the data set and stored in a separate file to be destroyed at the conclusion of the study and NIH mandated storage period. Survey personnel will receive training in protecting respondent confidentiality.

Consent regarding privacy

In order to enroll, participants will listen to a summary of the data storage and sharing policies in the study, and orally consent to those policies as a part of the informed consent procedure. Personally identifying information (PII) will be separated from all remaining data during the study. Following NIH policy, PII will be destroyed within three years of the conclusion of the study unless the participants request we keep their name and contact information on file for future studies.

Future use and release of data

De-identified data will enter the public domain after publication, given protocols which require this at many academic journals. No individually identifiable information will be shared or disseminated, including to the DSMB. At DSMB meetings, data and discussion are confidential. While aggregate statistics and reporting on individual SEAs will be undertaken, participant identifies will not be known to the DSMB members.

